Study Objective and Specific Aims	
The primary objective of this study is to evaluate safety and tolerability of the study product in adult and pediatric participants with PKAN.
 
The primary aims are:
 
• To compare safety or tolerability profiles of the study product between active and placebo groups over the 6-month double-blind parallel group phase of the study; and• To examine the long-term safety and tolerability profile of the compound over the 18-month (placebo group) -24-month (active group) active treatment period 
The primary hypothesis is that there will be no clinically significant difference in safety or tolerability profiles between active and placebo groups during six months of double-blind parallel study, nor between initial dose groups over 18-24 months of treatment with the study product.
 
The secondary aim is:
 
To evaluate the peripheral pharmacodynamic response of one component of a PKAN "molecular signature" (CoASY mRNA expression levels) in response to the study product.
 
The secondary hypotheses are that:
 
• CoASY mRNA expression levels will initially rise in all the study product-treated participants after 3 days ±2 days of treatment compared with placebo-treated participants; and• CoASY mRNA expression levels will subsequently decline in all participants after up to 18 months of study product treatment, consistent with secondary down-regulation of CoASY activity in the presence of excess substrate, (i.e. feedback inhibition); and

eIRB 18782 CoA-Z in PKAN (NIH)

	
There will be no difference in CoASY mRNA expression between initial treatment groups after up to 18 months of the single-dose active study product treatment. 
In a third exploratory aim, with the goal of informing future studies of the study product or other putative disease-modifying therapeutics, we will assess the feasibility of applying a latent growth curve (LGC) approach to natural history data collected before and during an intervention to detect disease-modifying effects.

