For modeling and inferential tests, we will consider a p-value less than 0.1 to be significant if the magnitude and precision of the estimated effect support that conclusion. Covariates will be specified in the description below. We will perform extensive exploratory data analysis and checks of model fit and will transform variables with obvious departures from normality.

Analysis of primary endpoints

Safety Analysis

Comparisons of participants experiencing treatment-emergent adverse events and clinically-significant abnormalities on clinical labs will be reviewed for clinical significance in the Safety Analysis dataset, which includes all participants who consume at least one dose of the study product. Events expected as part of the usual disease course in PKAN, whether present at trial enrollment or not, will not be considered or captured as adverse events.

Frequencies of participants experiencing at least one adverse event (AE) will be displayed by body system and preferred term according to *Medical Dictionary for Regulatory Activities* (MedDRA) terminology. Detailed information collected for each AE will include a description of the event; duration; whether the AE meets criteria as a Serious Adverse Event (SAE); severity / grade of the event; relationship to study product; changes made to the study product in response to the AE /SAE; and clinical outcome. Severity of the AEs will be graded according to the NCI *Common Terminology Criteria for Adverse Events*, Version 4.0. If the event meets criteria as an SAE, the nature of the SAE will be classified using standard FDA criteria.

The number and percentage of patients who experienced any serious AE (SAE), treatment-emergent AE, and treatment-emergent SAE will be summarized, as well as the total number of events per arm. AE data will be presented for months 0-6 and 7-37 and cumulatively, as appropriate. Emphasis in the analyses will be placed on AEs classified as treatment-emergent.

Clinically-significant abnormalities on clinical labs will be tabulated similarly to AEs. The number and percentage of patients experiencing clinically-significant abnormalities will be compiled in summary tables to examine the distribution by collection month [0-1-3-6-7-9-12-18-24 (25) months for the Primary Cohort; and 0-1-3-6-12-18 (19) months for the Open-label Cohort].

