As a final step, we will develop a **longitudinal model to characterize CoASY mRNA expression profiles over the entire 24-month study treatment period**. We plan to use a mixed effects model with random intercept and slope to account for correlation between measurements and to allow individuals to vary from the group mean. We will explore a number of possible parameterizations of the time effect, including fractional polynomials and splines. We will allow for different trajectories by (a) dose group and (b) PKAN type in separate models with a group x time interaction. This model will take the general form $CoASY_{ij} = \beta_0 + \beta_1 t_{ij} + \beta'_2 group + \beta_3 t_{ij} \times group + b_{1i} + b_{2i} t_{ij}$, where t_{ij} represents time on treatment in months (including partial months as decimals) and group indicates dose group or PKAN type, depending on the model.

Latent growth curve modeling plan for the exploratory aim will not be described here but is described in full in the protocol.

1. Protocol Title: A phase 2 study of a vitamin metabolite in PKAN

2. Objectives

The primary objective of this study is to assess the safety and tolerability of 4'-phosphopantetheine (4'-PPT), a product of intermediary metabolism, in pantothenate kinase-associated neurodegeneration (PKAN), an inborn error of vitamin B5 metabolism. The study product meets the FDA statutory definition for consideration as a medical food and is being developed as such for the nutritional management of PKAN.

The primary hypothesis is that there will be no clinically significant difference in safety or tolerability profiles between active and placebo groups during six months of double-blind parallel study, nor between dose groups over up to 18 months of treatment with 4'-PPT.

The primary aims are:

- To compare safety or tolerability profiles of 4'-PPT between active and placebo groups over the 6-month double-blind parallel group phase of the study; and
- To examine the long-term safety and tolerability profile of the compound over up to 18 months of open-label period.

The primary endpoints are:

- Safety outcome measures will include treatment-emergent adverse events and abnormalities on standard laboratory tests collected over up to 24 months of treatment.
- Tolerability outcomes will be assessed via participant retention in the study and adherence to the study product regimen.

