Pantothenate kinase-associated neurodegeneration (PKAN) is an inborn error of vitamin B5 metabolism. Children with the classic form of the disease suffer from a progressive neurodegenerative disorder that begins in the first few years of life, characterized by a severe movement disorder, cognitive and neuropsychiatric abnormalities, and pathologic iron accumulation in the basal ganglia of the brain. Children typically lose independent ambulation before age 10 and many die in the first decade of life. Those individuals who have disease onset later in life tend to have less severe manifestations but nonetheless suffer profound disability^[1,2]. Pathologically, the disease shows remarkable regional specificity in the brain, selectively affecting the globus pallidus, with very limited involvement of other regions^[3]. PKAN is an orphan disease, with a prevalence of 1-2 cases per million in the general population^[4], with higher prevalence reported in a few small populations where geographic, socio-economic, cultural or religious factors have resulted in founder mutations^[4,5]. Treatment options are currently limited to symptomatic management: there are no proven disease-modifying agents available.

b. PKAN Patients cannot metabolize vitamin B5 normally to make coenzyme A

PKAN is caused by mutations in the *PANK2* gene, which encodes one of four pantothenate kinase (PANK) enzymes in the human that serve to phosphorylate vitamin B5 in the rate-limiting step in coenzyme A (CoA) metabolism [Figure 1]. CoA is essential for the tri-carboxylic acid cycle, fatty acid oxidation and synthesis, amino acid metabolism and neurotransmitter synthesis, serving more than 9% of mammalian biochemical reactions^[6].

[figure not shown]

Figure 1: Coenzyme A metabolic pathway. Patients with mutations in the *PANK2* gene lack an enzyme to phosphorylate vitamin B5 (pantothenate) in selected regions of the brain in the key regulatory step in the coenzyme A (CoA) biosynthetic pathway. PPAT and DPCK together comprise the bi-functional enzyme CoASY. 4'-phosphopantetheine is a product of intermediary metabolism that is converted by CoASY into CoA.

c. Molecular and functional evidence of the disease is seen in the PANK2 knock-out mouse

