Comparisons of participants experiencing treatment-emergent adverse events and abnormalities on clinical labs will be reviewed for clinical significance in the Safety Analysis dataset, which includes all participants in the primary cohort who consume at least one dose of the study product. Events expected as part of the usual disease course in PKAN, whether present at trial enrollment or not, will not be considered or captured as adverse events.

Frequencies of participants experiencing at least one adverse event (AE) will be displayed by body system and preferred term according to *Medical Dictionary for Regulatory Activities* (MedDRA) terminology. Detailed information collected for each AE will include a description of the event; duration; whether the AE meets criteria as a Serious Adverse Event (SAE); severity / grade of the event; relationship to study product; changes made to the study product in response to the event; and clinical outcome. Severity of the AEs will be graded according to the NCI *Common Terminology Criteria for Adverse Events*, Version 4.0^[15]. If the event meets criteria as an SAE, the nature of the SAE will be classified according to standard FDA criteria.

The number and percentage of patients who experienced any serious AE (SAE), treatment-emergent AE, and treatment-emergent SAE will be summarized, as well as the total number of events per arm. AE data will be presented for months 0-6, 7-25 and cumulatively, as appropriate. Emphasis in the analyses will be placed on AEs classified as treatment-emergent.

Clinically-significant abnormalities on clinical labs will be tabulated similarly to AEs. The number and percentage of patients experiencing clinically-significant abnormalities will be compiled in summary tables to examine the distribution by collection month [0-1-3-6-7-9-12-18-24 +/- 25 months for the Primary Cohort; and 0-1-3-6-9-12-18 +/- 19 for the Open-label Cohort].

Graphic displays may be provided to illustrate the results over time. Initial review of group differences and determination of clinical significance will be performed by an unaffiliated physician familiar with the study population and blinded to treatment arm.

Tolerability Analysis

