Blood samples sent to OHSU for research biomarker testing will be received by study staff and re-labeled with a code number that does not contain any part of the 18 HIPAA identifiers. Study staff will generate a key to the codes that will be maintained by the study coordinator. This key will be restricted to the PI and study staff and will be kept secure on a restricted OHSU network drive in a limited access folder. [name] Lab staff will only have access to subject code numbers and will not be able to link back to names or other identifiers. Samples will be stored in the [name] lab freezer. The lab requires badge-access and is only accessible to those with permission. Samples will be stored until the study is complete. At that point, leftover samples will be transferred into the associated research repository established for this purpose and stored indefinitely.

Study data will be entered and stored electronically in a 21 CFR Part 11-compliant REDCap Cloud database, a web-hosted application hosted by nPhase (located in Encinitas, CA), an approved system that has been reviewed by OHSU security. Electronic files of safety lab data will be downloaded from Quest Diagnostics's secure portal periodically onto a secure OHSU server as a CSV or Excel file for upload to our REDCap Cloud database. Paper copies of safety labs and/or study product dose logs completed by subjects faxed or sent to the study site will be stored in a locked filing cabinet in an office that requires badge access. Upon receipt, standard institutional practices will be followed as described in the OHSU Information Security and Research Data Resource Guide to maintain the confidentiality and security of the data collected in this study. Study staff will be trained with regard to these procedures.

12. Provisions to Monitor the Data to Ensure the Safety of Subjects

See also separate Data Safety Monitoring Plan document. This study will have multiple levels of monitoring, including investigator-monitors, a medical safety monitor, and a full Data Safety Monitoring Board.

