The neurologist PI ([name]) and pediatrician-medical geneticist Co-I ([name]) who will act as real-time investigator-monitors in this clinical trial each have many years of experience conducting clinical studies in the vulnerable populations involved in the study. Their clinical and research careers have been dedicated to children and adults affected with inherited diseases. [name], a medical geneticist with extensive research and clinical experience in the management of children and adults with genetic and metabolic diseases, will serve as the independent medical safety monitor for this study. [name] will also serve as Chair of the Data Safety and Monitoring Board that will be convened prior to the start of the study, and which will meet on a scheduled and, if needed, *ad hoc* basis to review summary reports of the study progress and any adverse events that have occurred and will make formal recommendations based on these data as to whether to suspend, terminate or continue the research. The study team will follow OHSU's policy and procedures for inclusion of decisionally-impaired adults at: (<http://www.ohsu.edu/xd/about/services/integrity/policies/upload/di.pdf>).

The PI will review all adverse events in real-time, taking immediate action as needed in consultation with the clinical Co-I and Medical Safety Monitor. In addition, the PI will make a formal determination of seriousness and relatedness for each adverse event for data recording purposes and to meet reporting requirements, again consulting with the Medical Safety Monitor as needed.

13. Risks and Benefits

a. Risks to Subjects

Because it has not been studied in humans before, the study product poses unknown risks. However, our expectation is that toxicity will be very low for this high-purity compound that is identical to a naturally-occurring product of intermediary metabolism; which has shown no toxicity at all at high doses in mouse studies completed to date; and which is being dosed at "minimum effective" rather than the more usual "maximum tolerated" doses. The "minimum effective" dose derived from mouse studies turns out to be remarkably close to the molar equivalent of the recommended daily allowance (RDA) of the source vitamin pantothenate, which itself shows little toxicity even in doses far in excess of the RDA^[9]. The dose to be used in this study is within usual dietary intake ranges of the parent vitamin, pantothenate.

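### Events expected in the usual course of PKAN are not captured as adverse events even when they begin after dosing, so the AE and SAE tables cannot show an excess of them on active product

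*Combined protocol and SAP*

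**What the plan says.** The same sentence stands in the synopsis (Statistical Methods, Safety Analysis) and in protocol section 10.b (Safety Analysis). On what is recorded as an AE it says: "Events expected as part of the usual disease course in PKAN, whether present at trial enrollment or not, will not be considered or captured".

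Other parts of the plan bear on how this rule works:

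- **Seriousness depends on AE status.** Section 10.b states: "Detailed information collected for each AE will include a description of the event; duration; whether the AE meets criteria as a Serious Adverse Event". Section 12 adds that "the PI will make a formal determination of seriousness and relatedness for each adverse event for data recording purposes".
- **The disease picture is broad.** Section 4.a describes classic PKAN as including "a severe movement disorder, cognitive and neuropsychiatric abnormalities".
- **The first primary aim** (section 2) is to compare safety and tolerability "between active and placebo groups over the 6-month double-blind parallel group phase of the study". Treatment-emergent AEs are a primary safety outcome.
- **Judgement of safety.** The synopsis says safety is judged by clinical rather than statistical significance.
- **Blinding.** Section 10.e keeps the study team blinded to assignment.
- **Another document.** Section 12 says: "See also separate Data Safety Monitoring Plan document". That plan was not among the documents reviewed.

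**The concern.** Leaving stable, pre-existing symptoms off the AE form is ordinary practice. This rule goes further, because it also covers events that were absent at enrolment. Someone must decide, event by event, that a new problem is the disease and not the product. In a progressive disorder that question usually cannot be answered for one patient. The randomized placebo arm can answer it by group, but only in months 0-6 and only if the events are counted.

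Section 13.a says the product has not been studied in humans before and carries unknown risks. The primary hypothesis is that there is no clinically significant difference in safety. Dropping a class of events from both arms pushes the tables towards that hypothesis. Because this is a collection rule, no later analysis can bring the events back.

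**Working it through.** **Step 1. Follow one event through the text.** Suppose a participant has a new or worsened movement-disorder event at month 2 that is read as usual course.

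1. Sections 10.b and the synopsis: it is not captured as an AE, whether or not it was present at enrolment.
2. Section 10.b: seriousness, severity and relationship to product are details of an AE, so none of them is recorded.
3. Section 12: the investigator judges seriousness and relatedness for each adverse event, so this event is not judged.
4. Section 10.b: the tables of AEs, SAEs and total events per arm omit it. The blinded physician's review of group differences draws on the captured data, so it does not see the event either.

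No list of usual-course events, no named decision-maker and no exception for worsening or seriousness appears in the documents. Section 7.d shows that disease-type events can be serious: it mentions dystonic crises after travel that sometimes lead to hospital admission.

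**Step 2. Size.** The plan gives no safety event rate, margin or power, so there is no stated figure to reproduce. The following is an illustration.

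*Inputs from the documents:* 15 per arm with 1:1:1:1 allocation (section 10.a and synopsis), hence 15 placebo and 3 x 15 = 45 active. The 0.1 threshold is the one the synopsis gives for modeling and inferential tests. The plan does not apply it to safety.

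*Assumptions:* 20% of placebo and 50% of active participants have a new or worsened PKAN-type event in months 0-6. The rule removes the same share *s* of affected participants in each arm, which fits blinded classification.

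*Formulas:* expected placebo count = 15 x 0.20 x (1 - s); expected active count = 45 x 0.50 x (1 - s); visible difference = (0.50 - 0.20) x (1 - s). The chance of two-sided Fisher p<0.10 is the exact sum over all pairs of binomial counts.

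| Share removed | Placebo count | Active count | Visible difference | Chance of p<0.10 |
|---|---|---|---|---|
| 0 | 3 | 22.5 | 30 points | 64% |
| 50% | 1.5 | 11.3 | 15 points | 25% |
| 75% | 0.75 | 5.6 | 7.5 points | 5% |
| 100% | 0 | 0 | 0 | 0 |

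**Step 3. Vary the assumed rates**, with placebo at 20% and shares removed of 0 / 50% / 75% / 100%:

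- Active 40%: 35% / 14% / 2% / 0.
- Active 60%: 85% / 39% / 11% / 0.
- Active 50% at full enrolment (16 v 48): 66% / 27% / 7% / 0.

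For a smaller excess, 20% v 30%, the chance is only 13% even with full capture.

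**The case against.** **The rule covers only usual-course events.** An unusually severe or frequent event could be judged outside that course and recorded. This is true, but no criterion is given for that judgement, and the wording sets no limit for worsening. How much is lost therefore depends on an undefined term.

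**The Data Safety Monitoring Plan may handle serious events.** This stands as a limit. The finding concerns the protocol and SAP as supplied, and the analysis tables they describe would still need to be aligned with that plan.

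**Other data could show harm.** There are safety laboratory tests, a concomitant medication log, retention with exit reasons, adherence, and unscheduled visits for other clinically significant events. Participation in the natural history study is mandatory, and its functional trajectories are to be modelled with intervention group as a covariate. None of these is a count of events by arm. Unscheduled visits apply the same AE rule, and no by-arm medication table is planned. The natural history work is exploratory: "we will assess the feasibility of applying a latent growth curve (LGC) approach to natural history data collected before and during an intervention".

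**The study team is blinded.** Differential misclassification between arms is therefore not shown. The problem is lost sensitivity.

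**The rates are chosen, and safety is not tested.** Both points are correct. With 15 on placebo, moderate excesses are hard to see under any capture rule. The main point does not rest on the rates: a fully excluded event type is tabulated as 0 v 0 whatever happened.

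**There is no baseline symptom scale against which to judge worsening.** The schedule has none. Worsening would be judged against the medical history already taken at screening, which is imprecise but usable.

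**Conclusion.** The concern holds and must be fixed. As written, the plan removes post-dosing usual-course events from AE capture, and so from the SAE tables that depend on it, in the comparison that serves the first primary aim. The visible difference between arms equals the true difference times (1 - share removed). In the illustration a true 30-point excess shrinks to 15 points if half is removed and to nothing if all is removed.

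The direction of the effect and the zero at full exclusion follow from the text alone. The percentages rest on assumed event rates, equal removal in both arms, and a test the plan does not prescribe for safety. Confidence is medium, because the Data Safety Monitoring Plan was not seen and may contain an exception for serious events.

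**What to change.** Replace the sentence in both the synopsis and section 10.b with:

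> New-onset or worsened events (in frequency or severity relative to baseline), and all serious events, are recorded as adverse events in all arms even if expected in PKAN, with a disease-expected flag. They are tabulated by arm, severity and seriousness for months 0-6, both separately from and combined with other TEAEs. Stable pre-existing symptoms are recorded in medical history only.

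Also state whether the Data Safety Monitoring Plan already covers serious disease-expected events, and align the two documents. Because the combined table counts every event, an error in the flag moves an event between sub-tables but does not lose it.

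**Cost:** wording in two places, one field on the AE form and one extra table. No visits are added: the schedule already has AE calls at months 1, 3 and 6, or 3 x 64 = 192 post-baseline calls in the double-blind phase. The real downside in a progressive disease is more AE entries and longer listings with background events. If that burden is too high, capture of non-serious disease-expected events could be limited to the Primary Cohort in months 0-6, where the placebo contrast exists.

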This will be a single site, phase 2, safety and tolerability trial of 4'-phosphopantetheine (4'-PPT), a downstream product of intermediary metabolism in children and adults with PKAN, a inborn error of vitamin B5 metabolism. An initial 6-month, dose-ranging, parallel-group, randomized, double-blind, placebo-controlled phase will be followed by an 18-month, single-dose, open-label phase. There will be up to 2 months for screening and up to 2 months for follow up for up to a total of 28 months participation for this Primary Cohort. During the double-blind phase, participants in the Primary Cohort will be assigned randomly to one of three dose groups or placebo, with a 1:1:1:1 distribution. Once we meet our enrollment target for the Primary Cohort, we will shift additional enrollment directly into a single-dose open-label arm that will last up to 18 months per participant including up to 2 months for screening and up to 2 months for follow up. Our primary hypothesis is that there will be no clinically significant difference in safety or tolerability profiles between active and placebo groups during six months of double-blind parallel-group study, nor between dose groups over up to 18 months of treatment with 4'-PPT. Safety measures will include treatment-emergent adverse events collected at 10 time points and abnormalities on standard laboratory tests collected at 9 time points over 25 months (including follow up) for Primary Cohort participants. For the Open-label Cohort, treatment-emergent adverse events will be collected at up to 7 time points and safety labs at up to 6 time points over up to 20 months (including follow up). Participants will be stratified by PKAN type: classic or atypical, to ensure approximately equal distribution in each arm.

As a secondary, “proof of concept” aim, we will assess the pharmacodynamic profile of CoASY mRNA expression in the peripheral blood of participants receiving 4'-PPT or placebo. We will measure CoASY mRNA expression at 8 time points for the Primary Cohort and at up to 6 timepoints for the Open-label Cohort to examine four secondary hypotheses:

- a. **CoASY mRNA expression levels will rise in all 4'-PPT-treated participants after 1 month of treatment** compared with placebo-treated participants.

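### The long-term adverse-event tables use calendar windows only: the cumulative column dilutes an active-placebo difference, and months 7-25 do not align arms on time since first active dose

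*Combined protocol and SAP*

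**What the plan says.** Section 5 (Study Design) fixes one calendar for the Primary Cohort: "An initial 6-month, dose-ranging, parallel-group, randomized, double-blind, placebo-controlled phase will be followed by an 18-month, single-dose, open-label phase". Randomisation is 1:1:1:1 to three doses or placebo, and everyone takes the same assigned dose in the open-label phase.

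The synopsis (Study Objective and Specific Aims) states the second primary aim "over the 18-month (placebo group) -24-month (active group) active treatment period". Its primary hypothesis expects no clinically significant difference between active and placebo over six months, "nor between initial dose groups over 18-24 months of treatment with the study product". Section 2 (Objectives) words the same aim differently: "To examine the long-term safety and tolerability profile of the compound over up to 18 months of open-label period".

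The Safety Analysis in section 10.b summarises how many patients, and what percentage, had an event, "as well as the total number of events per arm". The windows are given as "AE data will be presented for months 0-6, 7-25 and cumulatively, as appropriate". The matching synopsis text reads "AE data will be presented for months 0-6 and 7-37 and cumulatively, as appropriate". Both add: "Emphasis in the analyses will be placed on AEs classified as treatment-emergent". No person-time denominator is planned, and nothing says whether, for a placebo starter, treatment-emergent is judged from the first dose of any product or from the first active dose.

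For the CoASY biomarker, by contrast, section 10.b resets placebo starters so that month 6 becomes their baseline, and the longitudinal model runs on time on treatment.

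**The concern.** The synopsis recognises that active exposure is unequal by initial arm and then sets a comparison across those arms. The planned tables carry no exposure information, and this has two consequences.

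- **Cumulative column.** For placebo starters it adds placebo time to active time. It is neither a placebo column nor an active one, so any excess of events on product is partly cancelled.
- **Months 7-25.** The windows are equally long, but placebo starters have just begun active product while the other arms have taken it for six months. An effect confined to the first weeks of exposure falls in this window for one arm and in months 0-6 for the other three.

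At stake is the second primary aim. The judgement is clinical and rests on displays, so a display that understates or misaligns a signal matters even though no formal test depends on it.

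**Working it through.** **Inputs from the documents.** 6 months double-blind, 18 months open-label, 15 evaluable participants per arm. The documents give no adverse-event rate, so the rates below are assumptions. The follow-up month after the last dose is the same in every arm and is left out.

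**Step 1. The plan's exposure figures.** Active starters: 6 + 18 = 24 active months. Placebo starters: 0 + 18 = 18 active months, plus 6 on placebo, so 24 months observed. This reproduces the synopsis's 18 and 24.

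**Step 2. Equal rates.** At 0.02 events per patient-month on both placebo and product, active starters expect 15 × 0.02 × 24 = 7.2 events and placebo starters 15 × 0.02 × (6 + 18) = 7.2. The share with at least one event is 1 − exp(−0.02 × 24) = 38.1% in both. There is no artefact in the cumulative column.

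**Step 3. Active rate k times the placebo rate.** The cumulative event ratio, active starters to placebo starters, is 24k / (6 + 18k), whatever the placebo rate. The counts and percentages below use a placebo rate of 0.02 per patient-month and 15 per arm.

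| k | Expected events, active vs placebo starters | Cumulative ratio | % with an event |
|---|---|---|---|
| 1 | 7.2 vs 7.2 | 1.00 | 38.1 vs 38.1 |
| 1.5 | 10.8 vs 9.9 | 36/33 = 1.09 | 51.3 vs 48.3 |
| 2 | 14.4 vs 12.6 | 48/42 = 1.14 | 61.7 vs 56.8 |
| 3 | 21.6 vs 18.0 | 72/60 = 1.20 | 76.3 vs 69.9 |

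However large k becomes, the ratio cannot exceed 24/18 = 1.33. The months 0-6 table shows the full ratio k.

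**Step 4. An early effect.** Suppose product adds 0.2 events per person in the first active month only (assumed). That is 15 × 0.2 = 3 extra events in each arm. Every arm eventually passes through that month, so the cumulative columns agree. Active starters have their 3 events in months 0-6. Placebo starters have theirs after the switch, when they are compared with arms in active months 7-24. The labels 0-6 and 7-25 also do not say where the weeks just after the switch belong.

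**Step 5. What person-time recovers.** With k = 2 and a placebo rate of 0.02, active starters give 14.4 / (15 × 24) = 14.4/360 = 0.04 per patient-month. Placebo starters on product give 10.8 / (15 × 18) = 10.8/270 = 0.04, and on placebo 1.8 / (15 × 6) = 1.8/90 = 0.02. The doubling that appeared as 1.14 is visible again, and the on-product rates agree across arms.

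**The case against.** A reader might infer that the active arms will show a third more events (24/18 = 1.33) merely because they were treated longer. The documents do not support this. The quoted table is cumulative over study time and does not leave out the placebo period. At one event per person-year, 15 active starters give 15 × 2 = 30 events, and 15 placebo starters give 15 × (0.5 + 1.5) = 30. The one-third gap would arise only in a tabulation restricted to active time, which section 10.b does not plan. It does show why treatment-emergent needs a definition: counting only events after the first active dose, with no denominator, would create that gap.

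The other defences have weight. Section 2 limits the long-term aim to the open-label period, which is equally long in every arm and at one assigned dose, and the separate windows fit that reading. If dose groups means the three active groups, as in the adherence analysis of section 10.d, exposure is equal even over 24 months. That reading is arguable, because the synopsis names the placebo group in the aim and section 5 uses initial dose groups to include placebo for CoASY. Laboratory abnormalities are tabulated by collection month, events are listed by participant and time point, the cumulative display is only as appropriate, and a blinded physician judges clinical significance.

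These safeguards limit the harm. They do not supply a comparison at equal time since first active dose, and a reviewer of raw group displays sees no exposure adjustment.

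**Conclusion.** The point stands as a weakness in how the long-term primary aim is summarised. It is not a demonstrated bias between arms with equal rates. The cumulative table turns a true doubling or tripling on product into event ratios of about 1.14 or 1.20, and the 7-25 window sets active months 1-18 against active months 7-24. The ratios rest on constant rates, full follow-up and assumed values of k. They do not depend on the placebo rate, but the percentages do. The randomised 0-6 month comparison is unaffected. Severity is low to moderate: the study is descriptive with about 15 per arm, individual listings exist, and the plan already applies the needed re-indexing to its biomarker.

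**What to change.** 1. Keep the months 0-6 table as planned.
2. For the long-term aim, add summaries by treatment actually received, indexed from each participant's first active dose: events per person-month on active product, and percent with an event (or Kaplan-Meier) over the first 18 active months in all four initial arms.
3. Define an event as treatment-emergent on active product relative to the first active dose, and always show it with person-time or at equal exposure.
4. Split the two periods at the date of the first open-label dose.
5. Use cumulative tables by initial arm for listing only.
6. Reconcile the long-term period in the synopsis with section 2, and the 7-37 window in the synopsis with 7-25 in section 10.b. Section 10.d also still refers to months 7-36 and month 37.

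The cost is analysis-plan wording and a few extra tables from dates already collected. The equal-exposure comparison has limits that should be stated beside it. It is not concurrent in calendar time, and it sets blinded months against open-label months. In the first six active months, only the mid-dose group has the same assigned dose as the placebo starters.
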